## INSTRUCTIONS: Complete Research Protocol (HRP-503)

- *Depending on the nature of what you are doing, some sections may not be applicable to your research. If so, you must provide the reason why the section is not applicable for the response. For example, most behavioral studies would answer all questions in section 30 with words to the effect of “drugs and medical devices are not used in this study.”*
- *When you write a protocol, keep an electronic copy. You will need to modify this copy when making changes.*
- *Do not remove the italics instructions or headings.*
- *If you are pasting information from other documents be sure to use the “Merge Formatting” paste option so that the formatting of the response boxes is not lost. If information is presented outside of the response boxes, it will not be accepted.*
- *If this study involves multiple participant groups who participate in different research procedures, consent processes, etc., be certain to provide information in each applicable section for each participant group and clearly label each participant group within a section or subsection.*

## **Grant Applicability:**

*Describe whether or not this protocol is funded by a grant or contract and if so, what portions of the grant this study covers.*

Response: N/A

## 1.0 Objectives

### 1.1 *Describe the purpose, specific aims, or objectives.*

Response: Type 1 diabetes is one of the most common chronic diseases of childhood. It is caused by autoimmune destruction of the insulin-producing pancreatic beta cells. Patients with Type 1 diabetes are at high risk for development of long-term complications related to hyperglycemia. Individuals with this disease are completely dependent on insulin for survival. While significant advances have been made in technological support for improving diabetes control, insulin remains the only effective treatment for Type 1 diabetes.

### 1.2 *State the hypotheses to be tested.*

Response: The main objective of this study is to test the hypothesis that a long-acting glucagon-like peptide 1 analog, liraglutide, will improve mean weekly blood sugars in adolescents and young adults with Type 1 diabetes.

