two drugs – exenatide (BID) and liraglutide (QD) are administered subcutaneously. They have been demonstrated to improve glycemic control in this population and, in some individuals, lead to sustained weight loss.

This study aims to determine whether acute exposure to liraglutide decreases the mean weekly blood glucose levels in adolescents with T1DM. In addition, we will determine whether liraglutide decreases glucose excursions following a meal challenge. *The overall hypothesis to be tested is that short-term exposure (7 days) to liraglutide improves glycemic control in adolescents/young adults with T1DM treated with continuous subcutaneous insulin infusion.*

**Specific Aim 1:** Determine whether liraglutide decreases the mean weekly blood glucose levels in adolescents/young adults with T1DM. *Hypothesis: Mean weekly blood glucose will decrease when liraglutide is used as an adjuvant therapy to insulin in individuals with T1DM.* Subjects will wear continuous glucose monitors to measure interstitial glucose as a surrogate for blood glucose. The CGM will be worn for 7 days pre- and post- daily liraglutide treatment. Data will be downloaded and mean weekly blood sugars will be determined.

**Specific Aim 2:** Determine whether liraglutide treatment decreases blood glucose excursion during mixed meal tolerance test in adolescents/young adults with T1DM. *Hypothesis: Post-prandial blood glucose excursions are attenuated with liraglutide treatment.* Mixed meal tolerance tests will be performed with and without pre-treatment with liraglutide. Blood glucose levels will be measured at set time points during the test and blood glucose excursions as well as blood glucose AUC in response to the meal challenge will be calculated.

**Specific Aim 3:** Determine whether glucagon secretion decreases during mixed meal tolerance test in subjects treated with liraglutide. *Hypothesis: Glucagon secretion following a meal challenge is suppressed in response to liraglutide treatment.* Serum samples will be drawn during mixed meal tolerance test performed with and without pre-treatment with liraglutide. Glucagon will be measured by ELISA and glucagon secretion AUC will be calculated.

**Specific Aim 4:** Determine whether liraglutide treatment leads to a reduction in total daily insulin dose.

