## **8.0 Procedures Involved**

### *8.1 Describe and explain the study design.*

**Response:** This is a pilot unblinded prospective within subject investigational-drug intervention trial.

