#### **Visit 1 Screening Day (day 0):**

- Review the subject's medical history and family medical history
- Review subject's blood sugars and insulin pump settings
- Measure height, weight, blood pressure and heart rate.
- The principal investigator will perform a physical exam.
- If hemoglobin A1c level is not recorded in the medical record within 2 weeks of visit 1, this test will be performed.
- Record mean total daily insulin dose (previous 72 hours) from insulin pump.
- Subjects will be advised to wear his/her continuous glucose monitor (CGM) for the next two weeks, changing sites as indicated by the manufacturer.
- For subjects who do not have a CGM, we will insert the Abbott Freestyle Libre Professional Device. This device will monitor glucose levels throughout the entire study period. Subjects will be advised to check blood sugars at least 4 times per day and at any occasion when symptoms of hypoglycemia develop.
- Subjects will be asked to keep a record of any episodes of hypoglycemia.
- Subjects will be asked to keep a 4 day food record (three days, 1 weekend day).
- Subjects will be advised to follow their usual diabetes care plan with respect to carbohydrate counting, diet and exercise.

**Visit 2 (Day 7):** Subjects will come fasting for this visit. They will bring the food records and diary of hypoglycemia to this visit. This visit will take approximately 4 hours. At this visit, the following procedures will be performed:

- Records of blood sugars and CGM data will be obtained from subjects wearing personal CGMs
- Subjects wearing the Freestyle LibrePro system will continue wearing the device unless it became dislodged during the study. A new device will be placed in this case.
- Blood sugars and insulin pump settings will be reviewed.
- Record mean total daily insulin dose (previous 72 hours) from insulin pump.
- A Mixed Meal Tolerance test will be performed (see below)

- Insulin pump settings will be adjusted to decrease the risk of hypoglycemia during liraglutide treatment. Basal rates will be decreased by 25% and meal boluses will be decreased by 33%.
- The first dose of liraglutide will be given at the study site. Subjects will be given 0.6 mg subcutaneously. Subjects will be taught how to use the delivery device at this visit.
- Subjects will be advised to take 0.6 mg of liraglutide subcutaneously every morning at about the same time.

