## **10.0 Data Management**

*10.1 Describe the data analysis plan, including any statistical procedures.*

*Response:* For statistical purposes, the **primary endpoint** of the study is to detect a difference between untreated and treated periods in the change from baseline in mean weekly blood glucose concentrations. The statistical analysis will be carried out using analysis of variance (ANOVA) and tested at the 0.05 level. The results will be computed as mean±SD.

The secondary end points based on glycemic changes will include the difference from baseline in standard deviations of the mean weekly glucose concentrations, mean fasting blood glucose concentrations, the duration of time spent in hyperglycemia ( $>150\text{mg/dL}$ ,  $>200\text{mg/dL}$ ,  $>250\text{mg/dL}$ ) and hypoglycemia ( $<70\text{mg/dL}$ ,  $<40\text{mg/dL}$ ), and insulin dosage. A reduction in the area under curve following the meal will constitute another secondary end point. Within subject comparisons of the magnitude of change from baseline will also be made for these glycemia related secondary endpoints using student's t-test. Comparisons for these and the primary endpoints will also be made using the paired t-test or Wilcoxon's test for paired data for each subject. Additional secondary end-points of the study will be change from baseline in 1) mean weekly blood glucose 2) glucagon area under the curve concentrations following meal challenge 3) change in daily insulin dose (total dose and units/kg) 4) caloric intake based on 4 day food records and 5) change in serum adiponectin and CRP levels before and after initiation of liraglutide treatment. The relation between change in postprandial sugars, glucagon, and total daily insulin dose will be studied by regression analysis to evaluate the relative contribution of each of these parameters to the improvement in post-prandial blood sugars

*10.2 Provide a power analysis.*

*Response:* A previous study (5) in adults with well-controlled diabetes demonstrated that liraglutide treatment decreased mean weekly blood sugars by 22 mg/dL. Based on these results, *a priori* power analysis indicates that 9 subjects will need to be enrolled in the study to detect a change in mean weekly blood sugars of  $22 \pm 20\text{ mg/dL}$  between untreated and treated periods with 80% power and alpha error of 0.05 (paired t-test). We will enroll up to 12 subjects for this study.

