Glucagon-like peptide 1 is an incretin hormone that is released in response to ingestion of food. Long-acting GLP-1 analogues and drugs which inhibit the metabolism of GLP-1 are FDA-approved as adjuvant therapy for the treatment of Type 2 diabetes. These drugs are currently not approved for use in the T1DM population. Individuals treated with GLP-1 analogues are at increased risk for hypoglycemia. It is recommended that patients treated with insulin secretagogue therapies (ie sulfonylureas), have their secretagogue dose decrease when GLP-1 analogue therapy is initiated. In this study, subjects have T1DM and are reliant on insulin for blood sugar control. In order to decrease the risk of hypoglycemia in this population, subjects will be counseled to decrease their basal insulin rates by 25% and their bolus insulin coverage for carbohydrates by 30% during the seven days when they are receiving liraglutide. All study subjects will be advised to check their blood sugar if they experience any symptoms consistent with hypoglycemia. They will be asked to contact the study team for persistent hypoglycemia while taking liraglutide. In addition, because insulin doses will be decrease significantly when liraglutide is initiated, there is the risk that subjects will experience hyperglycemia and may develop ketonuria. Subjects will be advised to contact the study team for persistent hyperglycemia and/or presence of urine ketones. The insulin dose will be increased to address this concern.

The most common side effects experienced by adults taking liraglutide include headache, nausea, and diarrhea. Nausea is most common when first starting liraglutide but generally decreases with time. Subjects may also feel less hungry while taking liraglutide. We will monitor for these and additional side effects during the study.

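### Liraglutide and a protocol-directed insulin reduction start at the same visit, so the glucose endpoints measure the combined regimen and not the drug

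*Combined protocol and SAP*

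**What the plan says.** Section 1.2 states the hypothesis as an effect of the drug: "liraglutide, will improve mean weekly blood sugars in adolescents and young adults with Type 1 diabetes". Specific Aim 1 (section 1.3) does the same, with the drug described as an adjuvant to insulin, and sets the measurement: "The CGM will be worn for 7 days pre- and post- daily liraglutide treatment".

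Section 8.1 calls the study a "pilot unblinded prospective within subject investigational-drug intervention trial". Section 8.2 fixes the order: an untreated week from Visit 1 to Visit 2, then a treated week from Visit 2 to Visit 3. Two things change at Visit 2 (Day 7):

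- "The first dose of liraglutide will be given at the study site".
- "Insulin pump settings will be adjusted to decrease the risk of hypoglycemia during liraglutide treatment". The size is given as "Basal rates will be decreased by 25% and meal boluses will be decreased by 33" (per cent).

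Section 13.1 repeats the reduction for the seven treatment days, but gives 30% for boluses. It warns that, because of the lower insulin doses, "there is the risk that subjects will experience hyperglycemia and may develop ketonuria", and says insulin will then be raised. Section 8.3 gives the purpose of the reduction as lowering hypoglycemia risk.

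Sections 7.1 and 10.1 define the primary endpoint as being to "detect a difference between untreated and treated periods in the change from baseline in mean weekly blood glucose concentrations". Time above 150, 200 and 250 mg/dL and time below 70 and 40 mg/dL are secondary endpoints, also taken as differences from baseline. Rates of hypoglycemia are a safety endpoint (end of section 7).

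**The concern.** The hypothesis names one cause, while the comparison contains two that begin together in every subject. By the protocol's own account the second cause acts on the endpoints. It is expected to push mean glucose and time above the thresholds up, against the hypothesis. It is intended to push hypoglycemia down.

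Two readings are therefore at risk. A null result or a rise in mean glucose could be taken as evidence that liraglutide does not work, when a real lowering may have been offset by less insulin. A change in time below 70 or 40 mg/dL, or in hypoglycemia rates, could be taken as a property of the drug. The reduction could produce a fall by itself, and it could also hide hypoglycemia that the drug causes. Section 14.1 says the results may be used to develop longer randomized, placebo-controlled trials, so a misreading would carry forward. The insulin-dose endpoint is not part of this point.

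**Working it through.** **What the contrast contains.** Write the treated-minus-untreated change in mean weekly glucose as

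change = D + C + R + P

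- D: effect of liraglutide.
- C: effect of the insulin reduction made at Visit 2 (expected to be positive, section 13.1).
- R: effect of any later insulin increase for hyperglycemia or ketones (section 13.1; amount and timing not given).
- P: anything else that differs between week 1 and week 2 (fixed order, unblinded, closer care).

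An indicator for the drug is 0 in week 1 and 1 in week 2 for every subject, and so is an indicator for the insulin reduction. The two columns are identical, so D and C cannot be estimated separately from these data.

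**Whether another analysis separates them.** Aim 4 relates insulin dose per kilogram to the change in glucose. The regression in section 10.1 relates postprandial glucose, glucagon and insulin dose. Delivered insulin will vary between subjects, but partly because insulin is raised in response to high glucose, so that variation does not recover C. Neither analysis isolates the drug.

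**Size of the reduction.** Assume basal insulin is 40% to 60% of the total and count the remainder as meal bolus (neither is in the documents).

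- Boluses at 33%: 0.4 × 25% + 0.6 × 33% = 29.8%; 0.6 × 25% + 0.4 × 33% = 28.2%.
- Boluses at 30%: 28.0% and 27.0%.

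The planned reduction is then about 27% to 30% of daily insulin.

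**The plan's sample size.** Inputs from section 10.2: change 22 mg/dL, 20 mg/dL read as the SD of the paired difference, alpha 0.05, 80% power, paired t-test. Sidedness is not stated; two-sided is used. Power comes from the noncentral t distribution with n − 1 degrees of freedom and noncentrality (22/20) × √n.

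- n = 8: 76.1%.
- n = 9: noncentrality 1.1 × 3 = 3.30, critical value 2.306, power 82.3%.
- n = 12: noncentrality 1.1 × 3.464 = 3.81, critical value 2.201, power 93.3%.

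The stated 9 reproduces.

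**Illustration of an offset.** Assume that 22 mg/dL is D at unchanged insulin, that C is a constant x all week, that R = P = 0 and that the SD stays at 20. The noncentrality becomes ((22 − x)/20) × √n. The entries are the chance of a significant fall.

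| Assumed x (mg/dL) | Net fall (mg/dL) | n = 9 | n = 12 |
|---|---|---|---|
| 0 | 22 | 82.3% | 93.3% |
| 5 | 17 | 61.0% | 76.4% |
| 10 | 12 | 35.4% | 47.5% |
| 15 | 7 | 15.1% | 19.7% |

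The documents give no value for x. An insulin increase under section 13.1 would shrink it.

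**The case against.** The strongest reply is that the plan already reads glucose together with insulin. Aim 1 speaks of adjuvant therapy, and Aim 4's hypothesis is that better control can be reached on less insulin, which is close to a combined-regimen proposition. This stands as evidence of intent. It does not change section 1.2, Aim 1 or the primary endpoint, and none of those mentions the imposed reduction.

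Second, the bias is conservative for the primary hypothesis, because the reduction works against a fall in glucose. That is right for the direction of C. A reader might go further and infer that a fall would therefore support the drug. The design does not allow that either: the order is fixed, there is no control, and section 14.1 expects subjects to receive intensified care with insulin adjustment.

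Third, a reader might infer that the plan sets out to credit liraglutide with less hypoglycemia. The documents do not say so. No aim claims it, section 13.1 expects GLP-1 analogs to increase the risk, and section 11.7 compares severe events with historical data. What stands is narrower: a difference from baseline in time below 70 or 40 mg/dL is a listed endpoint, and it cannot be assigned to either cause.

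Fourth, this is a pilot of up to 12 subjects and the reduction is a safety measure. Both are true. Neither prevents the objective from being worded to match what is measured.

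**Conclusion.** The point holds as one of attribution. The primary contrast and the threshold-time endpoints estimate the net change under liraglutide plus the protocol-directed insulin reduction, including any later insulin increases. They do not estimate the effect of liraglutide as worded in section 1.2 and Aim 1. This follows from the schedule and needs no numerical assumption.

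A reader might infer that a null result would be uninterpretable, or equally compatible with success and failure of the drug. That goes too far. The contrast can still describe the net before-after change under the regimen as given, and nothing in the documents assigns equal weight to the two explanations.

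A reader might also infer that the trial is underpowered. The sample-size arithmetic is sound on its own inputs. The drop to between 61.0% and 15.1% with 9 subjects, or between 76.4% and 19.7% with 12, is only an illustration. It rests on an assumed constant offset and on 22 mg/dL being the effect at unchanged insulin. The documents do not say whether insulin was reduced in the adult study behind that figure. If it was, 22 is already net and this power loss does not apply, but the attribution problem is unchanged.

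**What to change.** In section 1.2, Aim 1, section 7.1 and section 10.1:

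1. Define the tested quantity as the net within-subject change in mean weekly glucose, and in time above and below the thresholds, under liraglutide plus the protocol-directed insulin reduction compared with usual insulin.
2. Report delivered daily insulin for both weeks beside these results. The visit procedures record the previous 72 hours only, so the seven-day totals named in Aim 4 should be used.
3. State that no result in either direction, including hypoglycemia, will be attributed to liraglutide alone. A null or a rise will not be reported as absence of a drug effect. A fall will be reported as an uncontrolled before-after change under the combined regimen.

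Sections 8.2 (33%) and 13.1 (30%) on the meal-bolus reduction must be reconciled, because the reduction is part of the regimen being described. No insulin rule is proposed here.

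The cost is wording and one added summary of pump data already planned for collection. The downside is a less direct claim about the drug alone.

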### *Background*

### 1.3 *Describe the relevant prior experience and gaps in current knowledge.*

Response: **Background:** Type 1 diabetes (T1DM) affects approximately 1:500 children and represents the major form of diabetes in the pediatric population (1). Diagnosis of T1DM is based on symptoms consistent with hyperglycemia (polyuria, polydipsia, and weight loss) and elevated blood sugars. Diagnosis of T1DM is confirmed by measuring serum autoantibodies against insulin and other beta-cell proteins. Subcutaneous insulin is the mainstay of diabetes care; however, ability to achieve optimal glycemic control is impacted by multiple factors including diet, exercise, and psychosocial barriers.

The Diabetes Control and Complications Trial and follow-up EDIC trial were landmark studies demonstrating that improving glycemic control significantly reduces the risk of both micro and macro-vascular disease (2). While technologic advances in blood sugar monitoring, insulin analogs and insulin delivery devices have been made, it is estimated that less than 40% of individuals meet recommended glycemic standards as set forth by the American Diabetes Association; these estimates may be lower in the pediatric population. Thus, adjuvant pharmacologic therapies that improve glycemic control are being tested in patients with T1DM.

Incretin hormones are a class of intestinal peptides that are released in response to nutrient intake (3). The best described incretin hormones are glucagon-like peptide-1 (GLP-1) and glucose-dependent insulinotropic polypeptide (GIP). These hormones act at the level of direct stimulation of pancreatic  $\beta$ -cell function and through extra-pancreatic mechanisms. They primarily potentiate glucose-dependent insulin secretion from the  $\beta$ -cell; other  $\beta$ -cell effects include increasing insulin biosynthesis, stimulating  $\beta$ -cell replication, and preventing apoptosis. Secondary effects of incretin hormones include suppression of glucagon secretion, inhibition of gastric emptying, and potentiation of hepatic glucose uptake (3).

Currently, there are two GLP-1 analogs approved by the Food and Drug Administration as adjuvant treatment of Type 2 diabetes mellitus in adults ( $> 18$  years) who fail to reach glycemic targets with metformin and/or oral hypoglycemic agents. The

two drugs – exenatide (BID) and liraglutide (QD) are administered subcutaneously. They have been demonstrated to improve glycemic control in this population and, in some individuals, lead to sustained weight loss.

This study aims to determine whether acute exposure to liraglutide decreases the mean weekly blood glucose levels in adolescents with T1DM. In addition, we will determine whether liraglutide decreases glucose excursions following a meal challenge. *The overall hypothesis to be tested is that short-term exposure (7 days) to liraglutide improves glycemic control in adolescents/young adults with T1DM treated with continuous subcutaneous insulin infusion.*

**Specific Aim 1:** Determine whether liraglutide decreases the mean weekly blood glucose levels in adolescents/young adults with T1DM. *Hypothesis: Mean weekly blood glucose will decrease when liraglutide is used as an adjuvant therapy to insulin in individuals with T1DM.* Subjects will wear continuous glucose monitors to measure interstitial glucose as a surrogate for blood glucose. The CGM will be worn for 7 days pre- and post- daily liraglutide treatment. Data will be downloaded and mean weekly blood sugars will be determined.

**Specific Aim 2:** Determine whether liraglutide treatment decreases blood glucose excursion during mixed meal tolerance test in adolescents/young adults with T1DM. *Hypothesis: Post-prandial blood glucose excursions are attenuated with liraglutide treatment.* Mixed meal tolerance tests will be performed with and without pre-treatment with liraglutide. Blood glucose levels will be measured at set time points during the test and blood glucose excursions as well as blood glucose AUC in response to the meal challenge will be calculated.

**Specific Aim 3:** Determine whether glucagon secretion decreases during mixed meal tolerance test in subjects treated with liraglutide. *Hypothesis: Glucagon secretion following a meal challenge is suppressed in response to liraglutide treatment.* Serum samples will be drawn during mixed meal tolerance test performed with and without pre-treatment with liraglutide. Glucagon will be measured by ELISA and glucagon secretion AUC will be calculated.

**Specific Aim 4:** Determine whether liraglutide treatment leads to a reduction in total daily insulin dose.

*Hypothesis: Improved glycemic control can be attained with lower total daily insulin requirements in subjects treated with liraglutide.* Total daily insulin dose will be determined for seven days before and after initiation of liraglutide therapy. Insulin dose/kilogram body weight will be determined and evaluated in relationship to changes in mean weekly blood sugars.

In addition to the specific aims outlined above, the following exploratory aims will be addressed:

**Exploratory Aim 1:** Determine the side effect profile of liraglutide in adolescents/young adults with T1DM. *Hypothesis: Side effect profile of short-term liraglutide treatment in this population will be similar to that reported in adults.* Study subjects will keep a diary reporting hypoglycemic events and other potential adverse effects. Type, number, and rate of adverse events will be determined.

**Exploratory Aim 2:** Determine if there is a difference in caloric intake with liraglutide treatment in adolescents/young adults with T1DM. *Hypothesis: Caloric intake decreases in response to liraglutide treatment.* Subjects will keep a 4 day food record before and after initiation of liraglutide. Total caloric intake will be calculated, and within subject differences in caloric intake before and after liraglutide treatment will be determined.

**Exploratory Aim 3:** Determine if liraglutide treatment alters serum inflammatory markers in subjects with T1DM. *Hypothesis: Acute liraglutide therapy decreases serum levels of C-reactive protein and increases adiponectin levels in subjects with T1DM.* Serum samples before and after liraglutide therapy will be drawn and levels of inflammatory markers will be measured. Within subject differences will be determined.

Describe any relevant preliminary data.

Response: Although individuals with T1DM may not benefit from the direct  $\beta$ -cell actions of GLP-1 analogs given the targeted autoimmune component of the disease, the impact on glucagon secretion and extra-pancreatic effects may improve overall glycemic control in this population. At least two studies have reported data testing the efficacy of GLP-1 analogs in individuals with T1DM. Heptulla et al. reported significant reductions in glucose excursions following a standard meal test in adolescents and young adults (n = 8, age 13-22) treated with a single dose of exenatide (4). Varanasi et al. reported that mean weekly glucose levels decreased significantly in adults with well-controlled T1DM (mean HbA1c = 6.4%) treated with daily liraglutide for 1 week (5). These findings suggest that GLP-1 analogs may represent potential therapeutic adjuvants to improve glycemic control in patients with T1DM.

*1.4 Provide the scientific or scholarly background for, rationale for, and significance of the research based on the existing literature and how will it add to existing knowledge.*

Response: Optimal diabetes control decreases the risk of long-term micro- and macro vascular complications in individuals with diabetes. Currently the only FDA approved therapy for management of T1DM is insulin, delivered either subcutaneously or via inhalation. The addition of therapies to decrease risk of glucose excursions at mealtimes would offer significant benefits to diabetes care.

*1.5 Include complete specific citations/references.*

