## 7.0 Study Endpoints

7.1 *Describe the primary and secondary study endpoints.*

Response: For statistical purposes, the **primary endpoint** of the study is to detect a difference between untreated and treated periods in the change from baseline in mean weekly blood glucose concentrations. The statistical analysis will be carried out using

analysis of variance (ANOVA) and tested at the 0.05 level. The results will be computed as mean $\pm$ SD.

The secondary end points based on glycemic changes will include the difference from baseline in standard deviations of the mean weekly glucose concentrations, mean fasting blood glucose concentrations, the duration of time spent in hyperglycemia ( $>150\text{mg/dl}$ ,  $>200\text{mg/dl}$ ,  $>250\text{mg/dl}$ ) and hypoglycemia ( $<70\text{mg/dl}$ ,  $<40\text{mg/dl}$ ), and insulin dosage. A reduction in the area under curve following the meal will constitute another secondary end point. Within subject comparisons of the magnitude of change from baseline will also be made for these glycemia related secondary endpoints using student's t-test. Comparisons for these and the primary endpoints will also be made using the paired *t*-test or Wilcoxon's test for paired data for each subject. Additional secondary end-points of the study will be change from baseline in 1) mean weekly blood glucose 2) glucagon area under the curve concentrations following meal challenge 3) change in daily insulin dose (total dose and units/kg) 4) caloric intake based on 4 day food records and 5) change in serum adiponectin and CRP levels before and after initiation of liraglutide treatment. The relation between change in postprandial sugars, glucagon, and total daily insulin dose will be studied by regression analysis to evaluate the relative contribution of each of these parameters to the improvement in post-prandial blood sugars.

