#### **Visit 3**

- Insulin pump settings
- Total daily insulin dose
- Food diaries
- Download of continuous glucose monitor – mean weekly blood sugars
- Blood sugar records with reports of hypoglycemia
- Adverse effects
- Mean blood glucose excursion, glucagon release, and serum inflammatory markers during mixed meal tolerance test

*Describe any primary or secondary safety endpoints.*

**Response:** Adverse effects including nausea/vomiting, anorexia. Injection site reactions/pain. Rates of hypoglycemia. Clinical or biochemical evidence of pancreatitis.

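### The only source named for the hypoglycemia event rate is a self-report diary in an unblinded trial, with no event definition, although the sensor worn in both weeks could supply the count (minor)

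*Combined protocol and SAP*

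**What the plan says.** Exploratory Aim 1, in section 1.3, concerns the side-effect profile. It states "Study subjects will keep a diary reporting hypoglycemic events and other potential adverse effects" and then "Type, number, and rate of adverse events will be determined". Its hypothesis is that the profile will resemble the one reported in adults.

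The safety endpoints, listed after the Visit 3 variables in section 7, include "Rates of hypoglycemia". No data source, glucose threshold or duration is attached.

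Section 8.1 describes the design: "This is a pilot unblinded prospective within subject investigational-drug intervention trial". For the untreated week, section 8.2 (Visit 1) says "Subjects will be asked to keep a record of any episodes of hypoglycemia". At Visit 2 subjects receive a diary for hypoglycemia and other side effects, and are asked to tell staff about low readings that persist. Section 13.1 repeats that request: "They will be asked to contact the study team for persistent hypoglycemia while taking liraglutide".

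Sections 7.1 and 10.1 make "the duration of time spent in hyperglycemia", and likewise in hypoglycemia (below 70 and below 40 mg/dL), a secondary endpoint compared within subject. Section 8.2 has every subject wear a sensor, personal or supplied by the study, through both weeks.

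**The concern.** A diary rate is the true event rate multiplied by the fraction of events that the subject notices and writes down. In an unblinded before-and-after design, the subject knows which week is the treated one, and in that week is given a side-effect diary and asked to call about persistent lows. If the recorded fraction moves between weeks, the diary rate moves with it even when the true rate does not.

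Detection also depends partly on the subject. The Visit 1 instruction is "Subjects will be advised to check blood sugars at least 4 times per day and at any occasion when symptoms of hypoglycemia develop", so some lows come to light only through a scheduled or symptom-prompted check.

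What is at stake is how the hypoglycemia rate will be read. Insulin is reduced when liraglutide starts, so the direction of any change in lows is an open question, and section 14.1 says the results may be used to develop larger trials. An event count that does not depend on the subject's attention could be taken from data already collected, but the plan does not take it.

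**Working it through.** The plan gives no figure for the hypoglycemia rate, so there is none to reproduce. The sample size of 9 in section 10.2 concerns mean weekly glucose and has no bearing here. The check sets the relevant sections side by side.

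1. **Source of the count.** Section 1.3 names the diary. The safety endpoint in section 7 names nothing. The Visit 2 and Visit 3 variable lists also include blood sugar records with hypoglycemia reports and a sensor download, but no rule turns either into an event.
2. **Definition of an event.** None is given: no threshold, minimum duration, separation between events or confirmation.
3. **Prompts by week (section 8.2).** Untreated week: record any hypoglycemia. Treated week: record any hypoglycemia, record other side effects, and notify staff of persistent lows. The hypoglycemia instruction itself is nearly the same. The difference lies in the two additions.
4. **Sensor coverage (section 8.2).** Both weeks are covered for personal and study-supplied devices. Unwillingness to wear one is an exclusion (section 2.1).
5. **Sensor use for lows (sections 7.1 and 10.1).** Only duration below 70 and 40 mg/dL is specified. The source is not named, but in practice a duration must come from the sensor. One long low and several short ones can give the same duration, so this endpoint does not give the number of events.
6. **Planned comparisons.** Exploratory Aims 2 and 3 state within-subject differences; Exploratory Aim 1 does not. Section 11.7 compares only severe hypoglycemia, with historical data, and names no test.

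The mechanism is simple arithmetic:

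apparent rate ratio = true rate ratio × (treated-week recorded fraction ÷ untreated-week recorded fraction)

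The documents give no recorded fractions, so the values below are assumptions that show direction only. With a true ratio of 1:

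- 50% untreated, 60% treated: 0.60 ÷ 0.50 = 1.20
- 75% untreated, 50% treated: 0.50 ÷ 0.75 = 0.67
- equal fractions: 1.00

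A simulation shows what would follow if someone did run a paired t-test on diary counts (two-sided 0.05). It assumed 12 subjects, Poisson counts, 2 to 7 true lows per subject-week, no true change, and 4,000 runs per setting. The chance of a false difference was about 5% with equal recording, 6–13% when recording went from 50% to 60%, and 17–45% when it went from 50% to 75%. These figures are conditional on a test that the plan does not state.

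**The case against.** The strongest reply is that an objective measure is already planned. Time below 70 and 40 mg/dL is a secondary endpoint, ranks above an exploratory aim, and is compared within subject. If diary counts rose through recording alone, time below range would not rise with them, and the discrepancy would be visible. This stands and is the main reason the point is minor. What remains is that duration is not a count, and the plan does not tie it to the safety endpoint or say how to read a disagreement.

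Four stronger readings are tempting, and the documents do not support them:

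- A reader might infer that recording alone could decide the safety conclusion. No untreated-versus-treated test of the diary rate is stated, and the sensor endpoint stands beside it.
- A reader might infer that the safety endpoint is defined by the diary. Section 7 names no source. The link runs only through Exploratory Aim 1.
- A reader might infer that the two weeks use different rules for recording lows. They do not. The treated week adds side-effect recording and a safety notification, which may raise attention but do not change what counts as an episode.
- A reader might infer that mixing meter users and personal-sensor users biases the within-subject change. The planned device is the same in both weeks, so this mainly affects the pooled rate and comparisons between subjects.

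It is also fair to say that a sensor cannot classify symptoms or severity, and that severe events are the only rate with a stated comparison. The diary is therefore still needed.

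**Conclusion.** The point holds as a minor one. The only source named for hypoglycemic events is an unblinded self-report diary, the safety endpoint has no event definition, and the treated week carries extra prompts. Any untreated-versus-treated reading of the diary rate, even a descriptive one, may therefore mix a change in lows with a change in noticing or recording them. The size and direction of that effect cannot be derived from the documents; the ratios and false-positive figures shown rest on assumed recording fractions and event rates. The conclusion assumes that the sensor is worn in both weeks as planned and that time below range is computed from it. For a pilot of up to 12 subjects with this sensor endpoint already in place, it is a worthwhile clarification and no threat to the trial's main result.

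**What to change.** In Exploratory Aim 1 (section 1.3), in sections 7.1 and 10.1, and in the safety endpoints:

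- Define the non-severe hypoglycemia rate as the number of sensor events below 70 mg/dL, and separately below 40 mg/dL, per 24 hours of sensor data.
- State one minimum duration for an event and one rule for separating successive events. Fix both before data are examined and apply them identically to both weeks. The documents offer no basis for particular values, so the investigator must choose and record them.
- Report the rate within subject, beside time below 70 and 40 mg/dL.
- In section 8.2, use the same hypoglycemia prompt in both weeks. Keep the diary for symptoms, assistance needed and severe events, including the historical comparison in section 11.7, and report diary counts descriptively.

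The cost is a few lines of wording and a small programming task on data already downloaded. There are two downsides. Sensor noise can create false events, although the same rule then applies in both weeks. Sensor events are also not directly comparable with self-reported rates in adults, so the diary rate should be kept for that comparison.
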